9.6. Sample Collection and Handling

The actual dates and times of sample collection must be recorded in the CRF or laboratory requisition form.

If blood samples are collected via an indwelling cannula, an appropriate amount (1 mL) of serosanguineous fluid slightly greater than the dead space volume of the lock will be removed from the cannula and discarded before each blood sample is taken. After blood sample collection, the cannula will be flushed with 0.9% sodium chloride, United States Pharmacopeia (USP) (or equivalent) and charged with a volume equal to the dead space volume of the lock.

Refer to the Time and Events Schedule for the timing and frequency of all sample collections.

Instructions for the collection, handling, storage, and shipment of samples are found in the laboratory manual that will be provided. Collection, handling, storage, and shipment of samples must be under the specified, and where applicable, controlled temperature conditions as indicated in the laboratory manual.

10. SUBJECT COMPLETION/ DISCONTINUATION OF STUDY TREATMENT/ WITHDRAWAL FROM THE STUDY

10.1. Completion

A subject will be considered to have completed the study if he/she is actively participating in the induction or optimization/maintenance phase when one of the following is reached:

- esketamine is approved in the respective country and accessible through the local healthcare system funding or until end of December 2022, whichever is earlier
- the company terminates clinical development of esketamine nasal spray for TRD in that country/region

10.2. Withdrawal from the Study

A subject will be withdrawn from the study for any of the following reasons:

- Lost to follow-up
- Withdrawal of consent (Note: See “Withdrawal of Consent” section below; this should only be selected as a reason for withdrawal if the subject does not agree to any further study assessments or procedures. If the subject is agreeable to further study assessments or procedures, another reason for withdrawal should be selected.) Lack of efficacy
- The investigator or sponsor believes (eg, that for safety or tolerability reasons such as an adverse event) it is in the best interest of the subject to discontinue the study. The subject does not meet criteria for continuing into the optimization/maintenance phase at the end of the 54135419TRD3008 induction phase.
- Violation of protocol procedures (determined on a case-by-case basis)
- The subject becomes pregnant
- Death

If a subject discontinues study drug and withdraws from the study before the end of the study, assessments should be obtained. Refer to Section 9.1.5 for further information on the EW or End of Study Visit.

If a subject misses a study visit in the optimization/maintenance phase without notifying the site of the reason, the site personnel will attempt to contact the subject to confirm if the subject is still interested in participating in the study and if so, to schedule their next visit. During this contact the information on adverse events and concomitant medication will be collected. These contacts will be repeated weekly until successful scheduling of the next dosing session or otherwise until discontinuation from the study (up to 4 contacts will be made).

If a subject is lost to follow-up, every reasonable effort must be made by the study site personnel to contact the subject and determine the reason for discontinuation/withdrawal. This should include at least 3 telephone calls, certified letters, email requests, etc. To ensure access to follow-up subjects, the study sites should attempt to obtain both primary and secondary telephone contact numbers (eg, home, work, and mobile phone numbers), as well as other contact information

(eg, email addresses) from subjects prior to dosing. In addition, the study site should emphasize the importance of follow-up information to the subject prior to dosing. The measures taken to follow up must be documented.

When a subject withdraws, the reason for withdrawal is to be documented in the CRF and in the source document. Study drug assigned to the withdrawn subject may not be assigned to another subject.

Withdrawal of Consent

Every effort will be made in the study to ensure withdrawal of consent is not selected as a reason for discontinuation when in fact the subject withdrew for an identifiable reason (eg, due to an adverse event or lack of efficacy).

Subjects who wish to withdraw from the study should be asked if they are agreeable to be contacted for further follow up (eg, early withdrawal visit, adverse event follow up). Subjects who are not agreeable to follow-up contact will be withdrawn from the study as “withdrawal of consent.” Subjects who no longer wish to take study drug but are agreeable to be contacted for follow up will be withdrawn from the study with the reason noted as “Other” and will specify the reason why.

For a subject who “withdraws consent”, it is recommended that the subject withdraw consent in writing; if the subject refuses or is physically unavailable, the study site should document and sign the reason for the subject’s failure to withdraw consent in writing and maintain it with the subject’s source records.

The investigator will be responsible for making all required notifications to the Institutional Review Board (IRB) or Independent Ethics Committee (IEC).

11. STATISTICAL METHODS

Statistical analysis will be done by the sponsor or under the authority of the sponsor. A general description of the statistical methods to be used to analyze the efficacy and safety data is outlined below. Specific details will be provided in the Statistical Analysis Plan (SAP).

11.1. Subject Information

The following analysis sets will be used to summarize efficacy and safety data.

- Full Analysis Set for Induction phase: will be defined as all subjects who receive at least one dose of esketamine nasal spray during this phase.
- Full Analysis Set for Optimization/Maintenance phase: will be defined as all subjects who receive at least one dose of esketamine nasal spray during this phase.

11.2. Sample Size Determination

No formal sample size calculation was performed as only subjects who have participated in the other Phase 3 studies may participate in this study.

11.3. Safety Analyses

Safety data for the induction phase and the optimization/maintenance phase will be presented separately for each phase as well as for the entire treatment period (induction and optimization/maintenance phase). The baseline for safety assessments will be defined in the Statistical Analysis Plan.

Cognitive Function

Computerized cognitive test battery and HVLT-R: Descriptive statistics of each of the cognitive domain scores and changes from baseline will be provided at each scheduled time point.

Adverse Events

The verbatim terms used in the CRF by investigators to identify adverse events will be coded using the Medical Dictionary for Regulatory Activities (MedDRA). Treatment-emergent adverse events are adverse events with onset during the treatment phase or that are a consequence of a pre-existing condition that has worsened since baseline. All reported adverse events with onset during the treatment phase (ie, TEAEs, and adverse events that have worsened since baseline) will be included in the analysis. For each adverse event, the percentage of subjects who experience at least 1 occurrence of the given event will be summarized.

Treatment emergent AEs of special interest will be examined separately grouped in the following categories: drug abuse, dependence and withdrawal, increased blood pressure, increased heart rate, transient dizziness/vertigo, impaired cognition, cystitis, anxiety, events potentially related to suicidality, hepatic adverse events, events related to renal disorders, and symptoms of dissociation persisting beyond the typical ≤ 2 hour post esketamine administration, as well as delirium, psychosis or mania.

Summaries, listings, datasets, or subject narratives may be provided, as appropriate, for those subjects who die, who discontinue treatment due to an adverse event, or who experience a severe or a serious adverse event.

Vital Signs

Descriptive statistics of body weight, temperature, pulse/heart rate, respiratory rate, pulse oximetry and supine blood pressure (systolic and diastolic) values and changes from baseline will be provided at each scheduled time point. Any treatment-emergent abnormalities will be listed.

Clinical Laboratory Tests

Laboratory data will be summarized by type of laboratory test. Markedly abnormal results (specified in the SAP) will be used in the summary of laboratory data. Descriptive statistics will be provided for each laboratory analyte at baseline and at each scheduled time point in each phase of the study. Changes from baseline results will be presented. Frequency tabulations of the abnormalities will be provided. Listings of subjects with markedly abnormal laboratory results will also be provided.

Electrocardiogram (ECG)

The effects on cardiovascular variables will be evaluated by means of descriptive statistics and frequency tabulations. These tables will include observed values and changes from baseline values.

Electrocardiogram data will be summarized by ECG parameter. Descriptive statistics will be calculated at baseline and for observed values and changes from baseline at each scheduled time point. Frequency tabulations of the abnormalities will be made.

The ECG variables that will be analyzed are heart rate, PR interval, QRS interval, QT interval, and QT interval corrected (QTc) according to Bazett's formula (QTcB) and Fridericia's formula (QTcF).^{3,65}

Descriptive statistics of QTc intervals and changes from baseline will be summarized at each scheduled time point. The percentage of subjects with QTc interval >450 msec, >480 msec, or >500 msec will be summarized, as will the percentage of subjects with QTc interval increases from baseline <30 msec, 30 to 60 msec, or >60 msec.

All important abnormalities in ECG waveform that are changes from the baseline readings will be reported (eg, changes in T-wave morphology or the occurrence of U-waves).

C-SSRS

Suicide-related thoughts and behaviors based on the C-SSRS will be summarized in incidence and shift tables. Separate endpoints for suicidal ideation and suicidal behavior will be defined and summarized descriptively.

Other Safety and Tolerability Questionnaires and Assessments

CGDAR and MOAA/S: Descriptive statistics of scores and their changes (and/or percent changes) from pre-dose or baseline will be summarized at each scheduled time point.

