2. OBJECTIVES, ENDPOINTS, AND HYPOTHESIS

2.1. Objectives and Endpoints

2.1.1. Objectives

The primary objective of this study is to assess the safety and tolerability of esketamine nasal spray in subjects with TRD, with special attention to the following:

- Potential long-term effects on cognitive function
- Treatment-emergent adverse events (TEAEs), including TEAEs of special interest
- Post dose effects on heart rate, blood pressure, respiratory rate and blood oxygen saturation
- Potential effects on suicidal ideation/behavior

Secondary Objective

The secondary objective is to assess long-term efficacy, including effects on:

- Depressive symptoms (clinician and self-reported),

- Overall severity of depressive illness,
- Functioning and associated disability,
- Health-related quality of life and health status,

Exploratory Objectives

The exploratory objectives are to assess:

- Medical resource utilization
- Response remission rates to a second induction phase in eligible subjects who had relapsed in study ESKETINTRD3003
- Subject treatment satisfaction
- Subject tradeoff preferences for key benefit and harm outcomes associated with TRD treatment, using a stated-choice preference survey

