4.2. Exclusion Criteria

Any potential subject who meets any of the following criteria will be excluded from participating in the study.

1. Criterion modified per Amendment 3
 - 1.1 The evaluation of the benefit versus risk of continued esketamine nasal spray treatment is not favorable for the subject in the opinion of the investigator.
2. Since the last study visit in the subject's prior study, subject has suicidal ideation with intent to act per the investigator's clinical judgment or based on the C-SSRS [corresponding to a response of "Yes" on Item 4 (active suicidal ideation with some intent to act, without specific plan) or Item 5 (active suicidal ideation with specific plan and intent) in the suicidal ideation module of the C-SSRS] or suicidal behavior per the investigator's clinical judgment or based on the C-SSRS (corresponding to any score higher than 0 in the suicidal behavior module of the C-SSRS).
3. Criterion modified per Amendment 1
 - 3.1 Subject has:
 - A neurodegenerative disorder (eg, Alzheimer's disease, vascular dementia, Parkinson's disease), or evidence of mild cognitive impairment (MCI).
4. Subject has ongoing evidence of uncontrolled hypertension defined as a supine SBP >140 mmHg or DBP >90 mmHg predose on the day of the first intranasal treatment session. For those ≥ 65 years uncontrolled hypertension is defined as a supine SBP >150 mm Hg or DBP >90 mm Hg.
5. Subject has positive test result(s) for drugs of abuse (including barbiturates, methadone, opiates, cocaine, phencyclidine, and amphetamine/methamphetamine) predose on the day of the first intranasal treatment session.
6. Subject has any anatomical or medical condition that, per the investigator's clinical judgment based on assessment, may impede delivery or absorption of intranasal study drug.
7. Subject has taken any prohibited therapies that would not permit administration of the first intranasal treatment session, as noted in Section 8 (Pre study and Concomitant Therapy) and [Attachment 1](#).
8. Subject is a woman who is pregnant, breast-feeding, or planning to become pregnant while enrolled in this study or within 6 weeks after the last dose of intranasal study drug.

9. Subject has any condition or situation/circumstance for which, in the opinion of the investigator, participation would not be in the best interest of the subject (eg, compromise the well-being) or that could prevent, limit, or confound the protocol-specified assessments.

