6.6. Other Safety Parameters

6.6.1. Columbia-Suicide Severity Rating Scale (C-SSRS)

The C-SSRS⁷ is a low-burden measure of the spectrum of suicidal ideation and behavior that was developed in the National Institute of Mental Health Treatment of Adolescent Suicide Attempters Study to assess severity and track suicidal events through any treatment. It is a semi structured clinician-administered questionnaire designed to solicit the occurrence, severity, and frequency of suicide-related ideation and behaviors during the assessment period. Using the C-SSRS, potentially suicide-related events will be categorized using the following scores:

Suicidal Ideation (1-5)

- 1: Wish to be Dead
- 2: Non-specific Active Suicidal Thoughts
- 3: Active Suicidal Ideation with Any Methods (Not Plan) without Intent to Act
- 4: Active Suicidal Ideation with Some Intent to Act, without Specific Plan
- 5: Active Suicidal Ideation with Specific Plan and Intent

Suicidal Behavior (6-10)

- 6: Preparatory Acts or Behavior
- 7: Aborted Attempt
- 8: Interrupted Attempt
- 9: Actual Attempt (non-fatal)
- 10: Completed Suicide

If no events qualify for a score of 1 to 10, a score of 0 will be assigned (0 = “no event that can be assessed on the basis of C-SSRS”). Higher scores indicate greater severity.

The summaries of the C-SSRS outcomes will be based on the Full analysis set for subjects who have at least 1 post-baseline C-SSRS measurement and a pre-treatment C-SSRS assessment.

A frequency distribution at each scheduled time point will be provided. Shifts from the Baseline value (described in Section 2.2) to the most severe/maximum score during each phase will be summarized.

The maximum score assigned for each subject will also be summarized into one of three broad categories: No suicidal ideation or behavior (0), Suicidal ideation (1 - 5), Suicidal behavior (6 - 10). Shifts from the Baseline value (described in Section 2.2) to the maximum category during each phase will be summarized.

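### The protocol promises separate suicidal-ideation and suicidal-behavior endpoints, but the SAP's per-phase C-SSRS tables use one combined maximum, so the ideation count means ideation without behavior

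*Protocol*

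**What the plan says.** Suicidality belongs to the primary objective. Protocol 2.1.1 lists "Potential effects on suicidal ideation/behavior" among four items for special attention. For the analysis, Protocol 11.3 makes two commitments, both repeated in the synopsis: "Suicide-related thoughts and behaviors based on the C-SSRS will be summarized in incidence and shift tables", and "Separate endpoints for suicidal ideation and suicidal behavior will be defined and summarized descriptively". Protocol 11 leaves the details to the SAP.

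SAP 6.6.1 scores ideation 1 to 5 and behavior 6 to 10 on one scale. It adds "If no events qualify for a score of 1 to 10, a score of 0 will be assigned" and "Higher scores indicate greater severity". It then plans three outputs:

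- a frequency table by visit;
- a shift table on the score: "Shifts from the Baseline value (described in Section 2.2) to the most severe/maximum score during each phase will be summarized";
- a summary and shift table on the category: "The maximum score assigned for each subject will also be summarized into one of three broad categories", namely none (0), ideation (1-5) and behavior (6-10).

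The baseline psychiatric-history table (SAP 4.1, Table 3) uses the same three categories. No output is described that counts ideation regardless of behavior over a phase.

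The instrument itself keeps the two modules apart. Exclusion criterion 2 (Protocol 4.2) applies ideation items 4 and 5 separately from behavior, the latter "corresponding to any score higher than 0 in the suicidal behavior module of the C-SSRS".

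**The concern.** A class formed from one joint maximum does not supply two separate endpoints. Every behavior score ranks above every ideation score, so a single behavior event in a phase fixes the subject's class as behavior, whatever ideation was recorded. The row labelled suicidal ideation then reports ideation without behavior, and the label does not say so. The error can go only one way: the ideation count is correct or too low.

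This matters because a reader of the safety results will want to know what percentage of subjects had any suicidal ideation during a phase, and what percentage had ideation with intent (items 4-5). The protocol treats those two items as serious enough to exclude a subject at entry. No planned per-phase table answers either question once some subjects have both ideation and behavior. The subjects missing from the ideation count are not lost from the report, since they stand in the more severe class, but their ideation is not counted.

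**Working it through.** The plan has no figure to reproduce. It states no hypothesis, no sample size calculation and no expected C-SSRS rates. The check applies the SAP rule to test profiles and then bounds the shortfall.

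**Step 1: the rule on test profiles.** The SAP class is the class of the highest score in the phase. The separate endpoints are any score 1-5 and any score 6-10.

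| Scores in one phase | Maximum | SAP class | Any ideation | Any behavior |
|---|---|---|---|---|
| Ideation 3 only | 3 | ideation | yes | no |
| Ideation 5 and behavior 9 at one visit | 9 | behavior | yes | yes |
| Ideation 4, then behavior 6 at a later visit | 6 | behavior | yes | yes |
| Behavior 9 only | 9 | behavior | no | yes |
| None | 0 | none | no | no |

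Rows two and three are missing from the SAP ideation class but belong in an any-ideation endpoint. The behavior column and the SAP behavior class agree in every row.

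**Step 2: size of the shortfall.** Let pI be the proportion with any ideation in the phase, pB the proportion with behavior, and q the proportion of those with behavior who also have ideation.

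- SAP ideation proportion = pI − q × pB
- Shortfall = q × pB, which cannot exceed pB
- Relative shortfall = q × pB / pI

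Assumed ranges, since the documents give none: pI 10-30%, pB 0.5-3%, q 50-100%.

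- Smallest shortfall: 0.5 × 0.5% = 0.25 points. Relative to pI = 30%: 0.25/30 = 0.8%.
- Largest shortfall: 1.0 × 3% = 3.0 points. Relative to pI = 10%: 3/10 = 30%.
- Middle case: of 1000 subjects, 200 have any ideation and 10 have behavior, 8 of them with ideation. The SAP class holds 200 − 8 = 192, a shortfall of 0.8 points, or 8/200 = 4%.

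**Step 3: items 4-5.** The same formula applies, with q now the share of subjects with behavior who also had item 4 or 5. If 2% truly had item 4 or 5 and 1% had behavior, q of 80-100% gives 2% − 0.8% = 1.2% down to 2% − 1.0% = 1.0%. These rates are also assumed.

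**Step 4: what the planned tables do bound.** Any ideation must lie between the ideation class and the sum of the ideation and behavior classes. In the middle case that is 192 to 192 + 10 = 202, around the true 200.

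**The case against.** The strongest reply is that much of the information survives elsewhere in the plan, and most of that reply stands.

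- Protocol 9.2 specifies the Since Last Visit version, so each visit is scored for its own interval, and SAP 6.6.1 tabulates frequencies by visit. A reader might infer that one behavior event removes the subject's ideation from every table, or hides later worsening for the rest of the phase. The documents do not support that. Ideation at a visit without behavior stays in that visit's table, including after a behavior event. Only the per-phase tables are affected.
- A reader might infer that items 4-5 cannot be seen at all. They can: the maximum-score shift table shows 4 and 5 for subjects without behavior, and the by-visit table can show them too. What is missing is their per-phase incidence regardless of behavior.
- A reader might take it that the SAP keeps one score per visit. It does not say so. It leaves open whether a visit with both is shown by its maximum or by each event.
- The adverse-event category for suicidality (SAP 6.1) lists suicidal ideation, suicidal behavior and suicide attempt as separate terms, so one does not displace another. These are adverse event reports, however, and do not supply the promised C-SSRS endpoint.
- The study is descriptive, the behavior count is right, and the ideation count is bounded by the same table.

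What the reply does not reach is the departure from the protocol. By-visit frequencies cannot be added up to the number of subjects with ideation in a phase, because the same subject may appear at several visits. Bounds are not the promised endpoint.

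**Conclusion.** The point holds, limited to the per-phase tables. Protocol 11.3 promises two endpoints; SAP 6.6.1 supplies one combined maximum with exclusive classes, and the resulting ideation count can only be too low. The shortfall equals the share of subjects with both ideation and behavior and is capped by the behavior percentage. Under assumed behavior of 0.5-3% it is at most about 3 percentage points and may well be smaller. A large relative understatement is a tempting headline: 5% ideation, 3% behavior and complete overlap would give 3/5 = 60%. That would require 60% of all subjects with ideation also to show behavior, and nothing in the documents supports such rates. The direction and the conflict between the documents rest on the text; only the size rests on assumption.

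**What to change.** In SAP 6.6.1, define two endpoints for each phase:

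1. Any ideation: any of items 1-5 at any post-baseline assessment in the phase, regardless of behavior, with its own 0-5 maximum and items 4-5 shown separately.
2. Any behavior: any score 6-10 in the phase, regardless of ideation.

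Give each an incidence table and a shift table from baseline to worst value. State how a visit with both ideation and behavior enters the by-visit frequencies. Keep the combined 0-10 maximum as a supportive table.

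The cost is SAP wording and a few additional tables. Exclusion criterion 2 already relies on both modules, so the data are collected and no new assessment is needed.
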